4.2.4.1 Efficacy and Toxicity Endpoints

We will use standard response criteria universally accepted for MDS: IWG 2006 (14). For toxicity we will use standard adverse reporting criteria including leukemia specific language (Refer to Appendix C in PDOL).

4.2.4.2 Biomarker Research

Correlative studies will be considered exploratory and will be performed whenever possible. This will be voluntary. Patients will have opportunity to refuse participation on these studies. If a patient's baseline correlative bone marrow or blood sample is not collected for any reason, no additional correlative bone marrow or blood samples will be collected on the patient. Additionally, any samples that are missed are not considered a protocol deviation.

Gene sequencing.

Patients will be consented for genomic analysis according to institutional guidelines. At MD Anderson, patients not consented through the Apollo program (PI [name]) will be offered consenting under protocol LAB01-473 at baseline and their genomes will be sequenced using the T300 platform. 5 cc of blood in a green tube will be required for this analysis.

These samples will be obtained at baseline and on Cycle 1 day 28 (+/- 3 days) (including analysis of the bone marrow) every 3 cycles thereafter, and at the time of best morphological response.

Immune assessment.

Tumor tissue, blood samples and bone marrow aspirate will be collected on a separate IRB approved laboratory protocol (PA13-0291) for immune monitoring under the supervision of the Immunotherapy Platform at MD Anderson Cancer Center. In tumor tissues, immunohistochemical studies will be performed to evaluate tumor and immunological cell markers such as CD4 and CD8 T cells. In peripheral blood, we will also evaluate tumor and immune cell populations including but not limited to CD4 and CD8 T cells in pre and post therapy samples.

Peripheral blood

Up to 150 mL (within 24 hours) of peripheral blood will be collected under an IRB-approved laboratory protocol (PA13-0291) for testing of biomarkers described in this clinical protocol at the following time points:

- At screening
- Prior to each dose of MK3475 (pembrolizumab) during the first 3 cycles
- At time of best morphological response
- At progression

Product: Pembrolizumab

Protocol/Amendment No.: 2016-0343 Amendment 3.4

The treating physician or designee will have the option to cancel the laboratory protocol collection for patient safety without protocol deviation.

Analysis of hematopoietic stem cell populations

We will also analyze the effect of therapy at the level of different stem cell compartments (15). This will be done in the laboratory of [name] at MD Anderson Cancer Center. This will be done at baseline and Cycle 1 Day 28 and then every 3 months thereafter.

Because we will use a number of different assays, the variability of which is not necessarily established, the intention of the correlative studies is not to draw statistical conclusions in terms of the optimal biological dose of the agents studied here. Rather, they should be considered pilot studies that will help understand the in vivo mechanism of action of the agents studied, and may help in the development of future studies of this or other combinations.

5.0 METHODOLOGY

5.1 Entry Criteria

5.1.1 Diagnosis/Condition for Entry into the Trial

Patients with MDS with at least Int-1 disease per IPSS criteria (16) will be enrolled in this trial.

5.1.2 Subject Inclusion Criteria

In order to be eligible for participation in this trial, the subject must:

1-Voluntary signed informed consent before performance of any study related procedure not part of normal medical care indicating that the patient is aware of the investigation and nature of this study in keeping with Institutional policies and with the understanding that the consent may be withdrawn with the subject at any time without prejudice to future medical care.

2-INT-1 or higher risk MDS defined by IPSS criteria (16).

3-More or equal than 18 years of age at the time of signing consent.

4-Patients can or cannot have receive prior therapy with hypomethylating agent but will be allocated to specific patient cohorts based on their prior exposure. Patients that had received prior hypomethylating agent therapy should have at least received 6 cycles of therapy and not achieved any response or had progressed after any given number of cycles.

5-ECOG performance of 0 to 1.

Product: Pembrolizumab

Protocol/Amendment No.: 2016-0343 Amendment 3.4

6-Male patients, even if surgically sterilized, should agree to practice effective barrier contraception for the entire study treatment period and through 120 days after the last dose of the study treatment or agree to completely abstain from heterosexually intercourse. Female patients who are postmenopausal for at least one year before the screening visit or are surgical sterile or if they are of child bearing potential must have a negative pregnancy test within 72 hours of treatment of the start date and agree to practice two effective methods of contraception forms at the same time from the time of signing the informed consent through 120 days of the last dose of the study treatment or agree to completely abstain from heterosexual intercourse.

7-Willingness and ability to comply with scheduled visits treatment plans, laboratory tests and other study procedures

8-Demonstrate adequate organ function as defined in Table 1, all screening labs should be performed within 10 days of treatment initiation.

Table 1 Adequate Organ Function Laboratory Values

System	Laboratory Value
Renal	
Serum creatinine OR Measured or calculated ^a creatinine clearance (GFR can also be used in place of creatinine or CrCl)	$\leq 2.0 \times$ upper limit of normal (ULN) OR $\geq 60 \text{ mL/min}$ for subject with creatinine levels $> 1.5 \times$ institutional ULN
Hepatic	
Serum total bilirubin	$\leq 2.0 \times$ ULN OR Direct bilirubin \leq ULN for subjects with total bilirubin levels $> 1.5 \times$ ULN
AST (SGOT) and ALT (SGPT)	$\leq 2.5 \times$ ULN OR $\leq 5 \times$ ULN for subjects with liver metastases

^aCreatinine clearance should be calculated per institutional standard.

9-Female subject of childbearing potential should have a negative urine or serum pregnancy within 72 hours prior to receiving the first dose of study medication. If the urine test is positive or cannot be confirmed as negative, a serum pregnancy test will be required.

10-Female subjects of childbearing potential should be willing to use 2 methods of birth control or be surgically sterile, or abstain from heterosexual activity for the course of the study through 120 days after the last dose of study medication. Subjects of childbearing potential are those who have not been surgically sterilized or have not been free from menses for > 1 year.

Product: Pembrolizumab

Protocol/Amendment No.: 2016-0343 Amendment 3.4

11-Male subjects should agree to use an adequate method of contraception starting with the first dose of study therapy through 120 days after the last dose of study therapy.

12-Patients must receive a minimum dose of azacitidine of 75mg/(m)(2) dose.

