3.0 OBJECTIVE(S) & HYPOTHESIS(ES)

3.1 Primary Objective(s) & Hypothesis(es)

Objective:

1-To assess the safety of the combination of azacitidine and MK3475 in patients with higher risk MDS.

2- To explore the clinical activity (response, survival effect) of the combination of azacitidine with MK-3475 in patients with higher risk myelodysplastic syndrome

Hypothesis: The hypothesis is based on the concept that prior exposure to azacitidine may trigger expression of PD1/PDL1 and therefore “prime” leukemia cells to the effect of immune check point inhibitors. This mechanism may also be involved in resistance to hypomethylating agents.

Product: Pembrolizumab

Protocol/Amendment No.: 2016-0343 Amendment 3.4

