4.0 BACKGROUND & RATIONALE

4.1 Myelodysplastic syndromes (MDS)

The myelodysplastic syndromes (MDS) are a group of heterogeneous malignancies that manifest clinically by peripheral cytopenias and an increase risk of transformation to acute myelogenous leukemia (AML). Patients with MDS are in general divided into those with lower risk disease and those with higher risk disease. The standard of care for most patients with high risk MDS is a hypomethylating agent such as azacitidine (1, 2). Data from the now classic aza-001 trial (1) suggest that hypomethylating agents are associated with improved survival compared to supportive care. Longer follow up and experience with these compounds indicates that a large majority of the patients treated with these agents will eventually lose response to the hypomethylating agents. This phenomenon is called hypomethylating failure. The survival of such patients is very poor estimated to be 4 to 6 months (3, 4). Therefore the need for new agents or combinations in patients with MDS both as front line (to improve survival and delay failure) and in patients with HMA failure to improve survival. It should be noted that at this moment there are no drugs approved for HMA failure MDS (2).

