A randomized international Phase III trial (Study 5-azacytidine PH GL 2003 CL 001) for higher-risk MDS patients, classified by FAB as RAEB, RAEB-T, or CMML with 0-29% marrow blasts, with an IPSS of Intermediate -2 or High by central pathology/cytogenetic review was recently reported.(12) Patients were randomized to 5-azacytidine (75 mg/m²/day x 7days in 28 day cycles) or conventional care regimens (CCR), where CCR was pre-selected by the Investigator as best supportive care (transfusions, antibiotics, and G-CSF for neutropenic infection), low-dose cytarabine (20 mg/m²/day x 14 days in 28 day cycles); or standard chemotherapy (conventional induction/consolidation). Patients were stratified by FAB/IPSS and randomized 1:1 to 5-azacytidine or CCR. This trial did not allow erythropoietin. Three hundred fifty eight patients (70% male) were randomized at 79 centers to 5-azacytidine (N=179) or CCR (N=179): best supportive care only (N=105, 59%), low-dose cytarabine (N=49, 27%), or standard chemotherapy (N=25, 14%). Median age was 69 years (range 38-88 years). The 5-azacytidine and CCR groups were comparable for baseline patient characteristics. At baseline, 95% of patients were higher risk: RAEB (58%), RAEB-T/WHO AML (34%), CMML (3%), and other (5%). By IPSS, 87% were higher risk: Intermediate -2 (40%), High (47%), and 13% Indeterminate/other. 5-azacytidine was administered for a median of 9 cycles; low-dose cytarabine for 4 cycles. Median follow-up

Product: Pembrolizumab

Protocol/Amendment No.: 2016-0343 Amendment 3.4

for the survival analysis was 21.1 months. 5-azacytidine demonstrated statistically superior overall survival compared to CCR, with a median overall survival of 24.4 months vs. 15 months for CCR (stratified log-rank $p=0.0001$, hazard ratio 0.58). Two-year survival approximately doubled in the 5-azacytidine arm compared to CCR: 51% vs. 26% ($p<0.0001$). 5-azacytidine was well tolerated with safety data consistent with previous reports.

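### Do primary objectives in higher-risk MDS need a matching definition or IPSS subgroup analysis when entry starts at IPSS Int-1?

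*Combined protocol and SAP*

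**What the plan says.** Section 3.1 states the first primary objective as "To assess the safety of the combination of azacitidine and MK3475 in patients with higher risk MDS". The second, on clinical activity, is also set "in patients with higher risk myelodysplastic syndrome".

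Section 5.1.1 gives the entry condition: "Patients with MDS with at least Int-1 disease per IPSS criteria (16) will be enrolled in this trial". Inclusion criterion 2 in section 5.1.2 repeats it as "2-INT-1 or higher risk MDS defined by IPSS criteria (16".

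Section 4.1 introduces the risk terms without a cut-point: "Patients with MDS are in general divided into those with lower risk disease and those with higher risk disease". The only text that ties the term to IPSS groups is section 4.1.1 (Azacitidine), which describes a cited phase III trial in patients "with an IPSS of Intermediate -2 or High by central pathology/cytogenetic review". It reports "At baseline, 95% of patients were higher risk" by FAB subtype and then "By IPSS, 87% were higher risk: Intermediate -2 (40%), High (47"%).

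Section 8.1 describes the patients simply as having MDS and attaches its decision rules to two cohorts, hypomethylating failure and previously untreated, of 20 patients each. Section 8.2 analyses everyone who received any dose. It summarises demographic and clinical characteristics, tests response against clinical characteristics with Wilcoxon or Fisher tests, and compares survival endpoints across important subgroups by log-rank test. It names no characteristic or subgroup.

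**The concern.** The objectives name one population and the entry criteria seem to admit a wider one. If higher risk means Int-2 or High, as in the cited phase III trial, then Int-1 patients fall outside the objectives but inside every primary estimate. The trial has no control group, so its response and toxicity rates can be interpreted only against a known patient mix. A conclusion about higher-risk MDS could then rest on a blend of Int-1 and higher groups. Because section 8 does not mention IPSS, nothing obliges the analysts to show the blend or to give results for Int-2/High patients alone.

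**Working it through.** **1. What the documents establish about the term.** The phase III description uses *higher risk* in two ways for the same patients. By FAB it counts RAEB 58% + RAEB-T/WHO AML 34% + CMML 3% = 95%. By IPSS it counts Intermediate-2 40% + High 47% = 87%. That is background on another trial, with two answers. The only trial-specific text that sets an IPSS level is the entry requirement of Int-1 or above. The documents therefore show an undefined label. They do not show that Int-1 lies outside it.

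**2. Does any design figure depend on IPSS group?** The inputs in section 8.1 are:
- hypomethylating failure: null ORR 5%, target 20%, prior Beta(0.1, 1.9), cut-off 0.99;
- untreated: null 50%, target 70%, prior Beta(1, 1), cut-off 0.95;
- toxicity in both cohorts: limit 30%, prior Beta(0.6, 1.4), cut-off 0.95.

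None refers to IPSS. All the printed results reproduce.
- *Boundaries.* Beta posterior probabilities at 5, 10 and 15 patients give toxicity limits of 4, 6 and 8. Futility limits are never, 0 and 0 (hypomethylating failure) and 1, 4 and 7 (untreated). These match Tables 8, 9, 11 and 12.
- *Early stopping.* P(stop) = 1 − P(no futility stop) × P(no toxicity stop), with response and toxicity independent. In the hypomethylating-failure cohort at ORR 20%, P(no futility stop) = 1 − 0.8^10 = 0.8926. At toxicity 30%, P(no toxicity stop) = 0.9156. So P(stop) = 1 − 0.8926 × 0.9156 = 0.183, and 0.1828 without intermediate rounding, as in Table 10. The untreated cohort at ORR 70% and toxicity 30% gives 0.1618, as in Table 13. All 50 cells of the two tables agree to four decimals.
- *Credible intervals.* With x responders among n patients and prior Beta(a, b), the posterior is Beta(a + x, b + n − x), and the interval is its 2.5% and 97.5% points. For 4/20, Beta(4.1, 17.9) gives 0.057 to 0.369. For 14/20, Beta(15, 7) gives 0.478 to 0.854. Section 8.2 prints (0.06, 0.37) and (0.48, 0.85).

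**3. What would a separate Int-2/High analysis give?** The Int-1 share is not stated. Assume 0%, 25% or 50%, which leaves 20, 15 or 10 Int-2/High patients per cohort. The same formula gives:

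| Quantity | n = 20 | n = 15 | n = 10 |
|---|---|---|---|
| ORR, hypomethylating failure (20%) | 4/20: 0.06–0.37 | 3/15: 0.04–0.39 | 2/10: 0.03–0.42 |
| ORR, untreated (70%) | 14/20: 0.48–0.85 | 10/15: 0.41–0.85; 11/15: 0.48–0.89 | 7/10: 0.39–0.89 |
| Toxicity (30%) | 6/20: 0.13–0.50 | 4/15: 0.09–0.50; 5/15: 0.13–0.56 | 3/10: 0.09–0.57 |

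Two counts appear at n = 15 where the rate does not give a whole number of patients.

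In the untreated cohort the full-cohort interval already covers both the null 0.50 and the target 0.70, so subsetting only widens it (0.38 to 0.50 at n = 10). In the hypomethylating-failure cohort the full-cohort lower limit, 0.057, just clears the null of 0.05. At 15 or 10 patients it does not (0.043 and 0.026), and the width grows from 0.31 to 0.40. No decision rule uses such a subset.

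**The case for a change.** The strongest case for acting is that the wording costs almost nothing to align. One phrase in two objectives would change, IPSS group would be named in section 8.2, and no new data would be needed. Reading criterion 2 as a definition of higher risk is not secure either, since it most naturally means Int-1 or any higher IPSS group and so sets eligibility only. And a Fisher or log-rank p-value does not promise a credible interval for Int-2/High patients.

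Part of this stands. The term is undefined, the objectives and the entry criterion are worded differently, and section 8.2 does not name IPSS. The consequence does not follow. Any reader of the results also has the entry criterion, which states the population outright. A baseline summary of clinical characteristics that omitted the one disease score required for entry would be odd practice, and the Int-1 share would appear there. If IPSS is among the characteristics tested, the response-by-group table behind Fisher's test already shows each group's response rate. Only the subset credible interval would be new, and the table above shows how little it could say.

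**Conclusion.** The mismatch is one of wording. The objectives use a label that the protocol does not define, while the entry criterion, which governs who is enrolled, is explicit. No estimate, boundary, operating characteristic or decision rule changes under either reading of the label. The gap in section 8.2 is one that analysts would sensibly fill by showing IPSS group at baseline and among the characteristics tested. A formal Int-2/High analysis on perhaps 10 to 15 patients per cohort could not separate null from target and would feed no decision.

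This rests on two assumptions: that IPSS group, required for entry, is recorded and reported with the other clinical characteristics, and that results are described for the population actually enrolled. The subset sizes are illustrative. The size and direction of any Int-1 effect on response or toxicity cannot be derived from the documents, and if no Int-1 patients enrol the question has no practical effect. No change to the plan is called for.

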5.1.3 Subject Exclusion Criteria

The subject must be excluded from participating in the trial if the subject:

1-Significant medical psychiatric cognitive or other conditions that may compromise the patient ability to understand the patient information to give informed consent to comply with the study protocol or to complete the study.

2-Any severe or concurrent disease or condition including uncontrolled systemic infection, congestive heart failure, angina pectoris or cardiac arrhythmia and autoimmune processes that in the opinion of the investigator would make the patient inappropriate for study participation.

3-Patients with known hypersensitivity to 5-azacitidine or MK3475 or any of their excipients.

4-Prior history of stem cell transplantation.

5-For patients in the relapse or refractory cohort, any other therapy not being a hypomethylating agent after HMA failure or more than 4 months since completion of last cycle of hypomethylating agent. Please note that hypomethylating agent may include second generation compounds such as SGI-110, oral decitabine or oral azacitidine and will also include combinations with investigational agents.

6-Treatment with other investigational agents including chemotherapy, immunotherapy, or radiation therapy within a month prior to the start of this clinical trial

7-Is currently participating and receiving study therapy or has participated in a study of an investigational agent and received study therapy or used an investigational device within 4 weeks of the first dose of treatment.

8-Has a diagnosis of immunodeficiency or is receiving systemic corticosteroid therapy or any other form of immunosuppressive therapy within 7 days prior to the first dose of trial treatment. Physiologic doses of corticosteroids may be allowed for patients with adrenal insufficiency eligible.

9-Has a known history of active TB (Bacillus Tuberculosis).

Product: Pembrolizumab

Protocol/Amendment No.: 2016-0343 Amendment 3.4

10-Has had a prior anti-cancer monoclonal antibody (mAb) within 4 weeks prior to study Day 1 or who has not recovered (i.e., \leq Grade 1 or at baseline) from adverse events due to agents administered more than 4 weeks earlier.

11-Has had prior chemotherapy, targeted small molecule therapy, or radiation therapy within 2 weeks prior to study Day 1 or who has not recovered (i.e., \leq Grade 1 or at baseline) from adverse events due to a previously administered agent.

- Note: Subjects with \leq Grade 2 neuropathy are an exception to this criterion and may qualify for the study.
- Note: If subject received major surgery, they must have recovered adequately from the toxicity and/or complications from the intervention prior to starting therapy.

12-Has a known additional malignancy that is progressing or requires active treatment. Exceptions include basal cell carcinoma of the skin or squamous cell carcinoma of the skin that has undergone potentially curative therapy or in situ cervical cancer.

13-Has known active central nervous system (CNS) metastases and/or carcinomatous meningitis. Subjects with previously treated brain metastases may participate provided they are stable (without evidence of progression by imaging for at least four weeks prior to the first dose of trial treatment and any neurologic symptoms have returned to baseline), have no evidence of new or enlarging brain metastases, and are not using steroids for at least 7 days prior to trial treatment. This exception does not include carcinomatous meningitis which is excluded regardless of clinical stability.

14-Has active autoimmune disease that has required systemic treatment in the past 2 years (i.e., with use of disease modifying agents, corticosteroids or immunosuppressive drugs). Replacement therapy (e.g., thyroxine, insulin, or physiologic corticosteroid replacement therapy for adrenal or pituitary insufficiency, etc.) is not considered a form of systemic treatment.

15-Has known history of, or any evidence of active, non-infectious pneumonitis.

16-Has an active infection requiring systemic therapy.

17-Has a history or current evidence of any condition, therapy, or laboratory abnormality that might confound the results of the trial, interfere with the subject's participation for the full duration of the trial, or is not in the best interest of the subject to participate, in the opinion of the treating investigator.

18-Has known psychiatric or substance abuse disorders that would interfere with cooperation with the requirements of the trial.

Product: Pembrolizumab

Protocol/Amendment No.: 2016-0343 Amendment 3.4

19- Is pregnant or breastfeeding, or expecting to conceive or father children within the projected duration of the trial, starting with the pre-screening or screening visit through 120 days after the last dose of trial treatment.

20-Has received prior therapy with an anti-PD-1, anti-PD-L1, or anti-PD-L2 agent.

21-Has a known history of Human Immunodeficiency Virus (HIV) (HIV 1/2 antibodies).

22-Has known active Hepatitis B (e.g., HBsAg reactive) or Hepatitis C (e.g., HCV RNA [qualitative] is detected).

23-Has received a live vaccine within 30 days of planned start of study therapy.

Note: Seasonal influenza vaccines for injection are generally inactivated flu vaccines and are allowed; however intranasal influenza vaccines (e.g., Flu-Mist®) are live attenuated vaccines, and are not allowed.

